## **Population:**

265 COVID-19 PCR confirmed patients with indication for antiviral therapy is included in this study and will be randomized (2:1:1) into 3 groups

1- Group A: REGN3048-3051(Antibodies cocktail (casirivimab and imdevimab) )

2-group B: Remdesivir

3-group C: Favipravir

Population in this study are patients hospitalized in isolation hospital- Mansoura university.

A computer file containing a written informed consent from included patients will be provided. Paper will not be a tool for providing agreement by patients or their relatives to avoid transmission of infection.

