## **Interventions:**

Population included in this study will be assigned into 3 groups with 1:2:2 ratios to receive either antibodies cocktail or standard antiviral therapy (remdesvir, favipravir) as shown in table2 and figures 2 & 3.

Group A patients will receive REGN3048-3051(Antibodies cocktail (casirivimab and imdevimab) ) in low-dose regimen 1.2 gm (1200 mg of combined antibodies) diluted in 250 ml 0.9% sodium chloride solution as single I.V infusion over 30-60 minutes.

Group B patients will receive Remdesivir :

Day1 (loading dose): 200 mg (two 100mg vials) diluted in 500ml 0.9% sodium chloride solution infused I.V over 60 minutes

Day 2-5 or Day 2-10 (maintenance dose): 100 mg (one 100mg vial) in 250 ml 0.9% sodium chloride solution infused I.V over 30 minutes

Group C patients will receive Favipravir :

[figure not shown]
Day 1 (loading dose): 1600 mg (8 tablets) or 1800 mg (9 tablets) orally or in Ryle tube / 12 hours

Day 2-5 or day 2-10 (maintenance dose): 600 mg (3 tablets) or 800 mg (4 tablets) orally or in Ryle tube / 12 hours

[figure not shown]
Patients will be received standard of care by Physicians, Clinical pharmacist , Nurses and as guided by Egyptian COVID-19 treatment protocol.

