## **Statistical Analysis Plan (SAP):**

Intention-to-treat strategy will be used in this study. Intention-to-treat strategy will be used in this study. Statistical analysis will be achieved with SPSS, version 26.

Categorical variables will be presented as proportion and percent. Continuous variables will be presented as mean (standard deviation) for parametric data or as a median (25th-75th percentile) for non-parametric data.

Regarding baseline characteristics, Kruskal-Wallis or ANOVA test (depending on type of data and the continuous data distribution (normal or not)) will be used to compare these characteristics between the study groups. We will report the P-value for our statistical tests with level of statistical significance will be P-value  $\leq 0.05$ .

In case of existing differences in some baseline characteristics, logistic regression will be performed. This allows studying the effect of these variables on the primary outcomes of the study to exclude the effect of these confounding variables and to ensure the effect on the outcomes is due to interventions.

Regarding the outcomes, we will compare the 28-day all-cause mortality rate, result of PCR test at hospital discharge and incidence of infusion related or hypersensitivity reactions during and after the end of drug infusion (primary outcome) using the Kruskal-Wallis test with reporting the P-value.

While the secondary outcomes (hospital stay duration, icu stay duration and others) are compared using Kruskal-Wallis or ANOVA test depending on type of data and the distribution of data (normal or not)

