## **Sample Size:**

A total sample sizes of 246 patients would achieve at least 80 % power to detect a risk difference of 0.2 (20%) in the 28-day all-cause mortality (primary outcome) with a significance level ( $\alpha$ ) of 0.05 and 95% confidence level using the ANOVA or Kruskal-Wallis test of independent proportion in G\*Power software. To compensate for the estimated loss-to-follow-up and increase the study power, we will increase the sample size in both remdesivir and favipravir groups to be 106 patients compared to 53 patients in Antibodies cocktail Group As Antibodies cocktail product is available for only about 50 COVID-19 patients. In addition, the ratio (1:2:2) is the closest to reality according to number of patients who receive each drug.

The mortality data was estimated from the average mortality in August, September, and October 2021 at the Mansoura University Isolation Hospital among all hospitalized patients. Mortality rate is found to be about 360 cases in these 3 months (120 cases / month). The online system has been used to obtain mortality rate in these three months.

The current admission rate at the Mansoura University – Isolation Hospital is 250 cases per month on average; our needed sample is about 250 cases.

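### ANOVA for the secondary outcomes is chosen on normality alone with arms of 53/106/106; naming Welch's ANOVA protects the 5% level at almost no cost if spread differs between arms

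*Combined protocol and SAP*

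**What the plan says.** Under Statistical Analysis Plan, secondary outcomes such as hospital and ICU stay "are compared using Kruskal-Wallis or ANOVA test depending on type of data and the distribution of data (normal or not"). Data type and normality are the only criteria. Equal variance is not mentioned, no Welch or other unequal-variance version is named, and there is no fallback. The threshold is stated once for all tests: "level of statistical significance will be P-value" at most 0.05.

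The Sample Size section sets the remdesivir and favipiravir groups "to be 106 patients compared to 53 patients in Antibodies cocktail Group", because the cocktail supply covers only about 50 patients. Table 2 gives the same counts, and Interventions agrees: "Population included in this study will be assigned into 3 groups with 1:2:2 ratios". The Population section says something else. There the sample "is included in this study and will be randomized (2:1:1) into 3 groups", with the cocktail listed first, which would make it the largest arm.

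On spread, the plan says only how it will be reported: "Continuous variables will be presented as mean (standard deviation) for parametric data". No SD, and no expected difference in SD between arms, appears for any secondary outcome.

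**The concern.** Classical ANOVA assumes a common variance. With equal arms it tolerates moderate violations. With unequal arms it does not, because the pooled within-group variance is weighted towards the larger groups. If the small arm is the more variable, the pooled variance is too small for the comparison and the test rejects too often. If the small arm is the less variable, the test is conservative and misses real differences.

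The imbalance here is planned, at one to two. Unequal spread is possible: the trial admits moderate, severe and critical patients, the Method section calls it non-randomised, and the Sample Size section ties the ratio to how many patients receive each drug. The severity mix could therefore differ between arms, and the spread with it. At stake is whether a p-value of 0.05 means what it says for those secondary outcomes that are analysed by ANOVA.

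**Working it through.** **Inputs.** Arm sizes of 53, 106 and 106, total 265 (Sample Size, Table 2). Nominal level 0.05 (Statistical Analysis Plan). The ratio *s* of the cocktail SD to the SD of the other two arms is not in the documents. It is an assumption, varied from 0.5 to 3.

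**The plan's own figure.** For the primary outcome the plan states: "A total sample sizes of 246 patients would achieve at least 80 % power to detect a risk difference of 0.2 (20"%). One-way ANOVA power from the noncentral F distribution, with three equal groups, Cohen's f = 0.2 and level 0.05, has noncentrality N × f². At N = 246 this is 246 × 0.04 = 9.84 and power is 0.804; at N = 243 power is 0.798. So 246 reproduces. For the secondary tests the plan gives no error rate beyond the nominal 0.05.

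**Mechanism.** Set the SD of the other arms to 1 and assume equal means.

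- Expected between-group mean square: Σ(1 − nᵢ/N)σᵢ² / (k − 1) = (0.8s² + 0.6 + 0.6)/2 = 0.4s² + 0.6.
- Expected within-group mean square: Σ(nᵢ − 1)σᵢ² / (N − k) = (52s² + 210)/262.

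The F test is calibrated for a ratio of 1.

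- s = 1.5: 1.500 / 1.248 = 1.20
- s = 2: 2.200 / 1.595 = 1.38
- s = 0.5: 0.700 / 0.851 = 0.82

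With equal arms the ratio is 1 whatever the SDs.

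**False-positive rate.** Simulated with normal data, equal means, arms of 53/106/106 and 50,000 runs per setting:

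| s (cocktail SD / others) | Classical ANOVA | Welch's ANOVA |
|---|---|---|
| 0.5 | 3.2% | 4.9% |
| 0.67 | 3.6% | 5.1% |
| 1.0 | 5.0% | 5.0% |
| 1.1 | 5.5% | 4.8% |
| 1.25 | 6.6% | 4.9% |
| 1.5 | 8.6% | 5.1% |
| 2.0 | 12.1% | 5.2% |
| 3.0 | 16.4% | 5.1% |

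Other settings, classical ANOVA:

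- One 106-patient arm more variable, by 1.25 to 2 times: 4.5% down to 3.9%.
- Three equal arms of 88, s = 1.5 and 2: 5.2% and 6.0%.
- 2:1:1 with the cocktail arm largest (133/66/66), s = 1.5 and 2: 2.7% and 2.0%.

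**Power.** Simulated at 53/106/106 with 40,000 runs per setting and a shift in the cocktail mean, expressed in SDs of the other arms (the shifts are assumptions):

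- Shift 0.35, s = 0.5: ANOVA 63%, Welch 90%.
- Shift 0.35, s = 0.67: ANOVA 59%, Welch about 77%.
- Equal variances, shift 0.4: ANOVA 63.3%, Welch 62.8%.
- Equal variances, shift 0.5: ANOVA 83.3%, Welch 82.9%.

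**The case against.** A reader might infer that unequal spread will push the false-positive rate of the secondary comparisons to 9–12%. The documents do not support that, for four reasons.

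- **Size.** That range needs a cocktail SD 1.5 to 2 times the others', and no SD is given. At ratios of 1.1 to 1.25 the rate is only 5.5% to 6.6%.
- **Direction.** A less variable cocktail arm, or one more variable large arm, makes the test conservative. Mixed severity widens spread within every arm; it does not show that the arms differ, still less that the cocktail arm has the larger spread.
- **Scope.** Only outcomes judged normal go to ANOVA. Need for ventilation is binary, SOFA and the WHO score are ordinal, and durations, CRP, ferritin and LDH are bounded at zero and may well go to Kruskal-Wallis.
- **Allocation.** The Population section's 2:1:1 would reverse the direction if it governed.

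All four stand as limits on the claim. On the last, the explicit counts in Table 2 and Sample Size favour 1:2:2, but the sections must be reconciled.

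It can also be said that the plan writes only ANOVA, and Welch's version is an option in the SPSS one-way procedure. That does not answer the point: ANOVA without qualification, chosen on normality alone, will be read and run as the classical F test.

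Finally, the remedy leaves Kruskal-Wallis alone, and that test is not immune: with normal data it gives 6.7% and 8.1% at ratios of 1.5 and 2. This is true and limits what the fix achieves. It is not a reason to keep the classical F test.

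**Conclusion.** The point holds in conditional form. At the planned arm sizes, the rule for choosing ANOVA omits an assumption that matters. Classical ANOVA then runs anywhere from about 3% to about 12% at a nominal 5% for SD ratios between 0.5 and 2, with both the ratio and its direction unknown. Loss of power on the conservative side can be substantial. The figures rest on assumed SD ratios, normal data and arms of 53/106/106.

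This is not a demonstrated inflation of the trial's error rate. It does not touch the primary outcomes, which the plan sends to Kruskal-Wallis, and it concerns only those continuous secondary outcomes that reach ANOVA. It is a free or cheap improvement, not a defect that threatens the trial's main conclusions.

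**What to change.** In the Statistical Analysis Plan section, replace ANOVA with Welch's ANOVA for continuous secondary outcomes judged approximately normal. Apply it in all such cases and do not make the choice depend on a preliminary test of variances. If pairwise comparisons are made (none are specified at present), use Games-Howell.

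No change to the regression is needed on this account: the only regression in the plan is logistic and concerns the primary outcomes.

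Reconcile the allocation ratio in the Population section with Interventions, Table 2 and Sample Size, so that the arm sizes behind the analysis are unambiguous.

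The cost is one line in the plan and an option in the SPSS one-way procedure. No extra patients or data are needed, and the power given up when variances are equal is less than 1 percentage point.

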## **Sample Size:**

A total sample sizes of 246 patients would achieve at least 80 % power to detect a risk difference of 0.2 (20%) in the 28-day all-cause mortality (primary outcome) with a significance level ( $\alpha$ ) of 0.05 and 95% confidence level using the ANOVA or Kruskal-Wallis test of independent proportion in G\*Power software. To compensate for the estimated loss-to-follow-up and increase the study power, we will increase the sample size in both remdesivir and favipravir groups to be 106 patients compared to 53 patients in Antibodies cocktail Group As Antibodies cocktail product is available for only about 50 COVID-19 patients. In addition, the ratio (1:2:2) is the closest to reality according to number of patients who receive each drug.

The mortality data was estimated from the average mortality in August, September, and October 2021 at the Mansoura University Isolation Hospital among all hospitalized patients. Mortality rate is found to be about 360 cases in these 3 months (120 cases / month). The online system has been used to obtain mortality rate in these three months.

The current admission rate at the Mansoura University – Isolation Hospital is 250 cases per month on average; our needed sample is about 250 cases.

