## **Aim of the study:**

1-To evaluate the efficacy of antibodies cocktail (casirivimab and imdevimab) compared to standard antiviral therapy in reducing 28-day mortality in hospitalized patients with moderate, severe or critical COVID19

2-To evaluate safety of antibodies cocktail (casirivimab and imdevimab) compared to standard antiviral therapy by monitoring of hypersensitivity and infusion related reactions or other significant adverse effects

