### **Exclusion criteria**

Patient should not have any of the following to be included:

1-history of hypersensitivity or infusion related reactions after administration of monoclonal antibodies.

2-prior use of standard antiviral therapy (remedsvir or favipravir).

3-Current use of controversial antiviral therapy (hydroxychloroquine, ivermectin, nitazoxanide, oseltemavir, acyclovir, ribavirine, lopinavir/rotavirus, sofosbuvir, dectasevir, semipiravir, azithromycin).

4-patients expected to die within 48 hours.

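### The claimed 80% power for a 20-point mortality difference does not belong to the 53/106/106 design, which has about 66% at 48% comparator mortality, and the planned three-group test does not by itself answer aim 1

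*Combined protocol and SAP*

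**What the plan says.** - **Power claim (Sample Size).** "A total sample sizes of 246 patients would achieve at least 80 % power to detect a risk difference of 0.2 (20"%) in 28-day all-cause mortality, at a significance level of 0.05, by ANOVA or Kruskal-Wallis in G*Power. No mortality rate per group is given, and the section does not say which groups are assumed to differ.
- **Actual group sizes (Sample Size; Table 2).** 53/106/106, total 265. The cocktail group is small because "Antibodies cocktail product is available for only about 50 COVID-19 patients". To offset loss to follow-up and "increase the study power, we will increase the sample size in both remdesivir and favipravir groups to be 106 patients" each. No loss rate is given, and no power is given for this layout.
- **Mortality source (Sample Size).** "Mortality rate is found to be about 360 cases in these 3 months (120 cases / month") among all hospitalised patients in August to October 2021. The current admission rate "is 250 cases per month on average".
- **Aim 1 (Aim of the study).** The cocktail is evaluated "compared to standard antiviral therapy in reducing 28-day mortality".
- **Planned test (Statistical Analysis Plan).** The primary outcomes, including mortality, are compared across the three groups "using the Kruskal-Wallis test with reporting the P-value". Logistic regression follows only if baseline characteristics differ. No pairwise or pooled contrast is named.
- **Allocation.** The Population section gives 2:1:1. Interventions, Table 2 and Sample Size give 1:2:2.

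**The concern.** The section reads as though 246 patients secure 80% power and 265 secure a little more. Power in a three-group comparison depends on how patients are divided as well as on the total, and here the group of interest is the smallest. If 80% belongs to equal groups, a non-significant mortality result will be read as stronger evidence against a 20-point benefit than it is.

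The second problem is the target of the test. A three-group P-value asks whether any of the groups differ. Aim 1 asks whether the cocktail differs from standard therapy. A significant result can arise from a remdesivir-favipiravir difference alone, so it does not by itself support a statement about the cocktail.

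**Working it through.** **Inputs.** From the documents: N = 246, 80% power, difference 0.20, alpha 0.05, three-group Kruskal-Wallis test, groups 53/106/106. Comparator mortality is not stated. Sample Size implies a crude 120/250 = 48%, used here as an assumption and varied below. Following aim 1, the cocktail is taken to be 20 points below both comparators.

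**Step 1: reproduce 246.** One-way ANOVA, three equal groups, noncentral F with noncentrality N × f². With f = 0.20:
- N = 243: 243 × 0.04 = 9.72, power 0.798
- N = 246: 246 × 0.04 = 9.84, power 0.804

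So 246 is the smallest balanced total reaching 80%, with 82 per group. A two-proportion calculation for 40% versus 20% also gives 82 per arm (3 × 82 = 246). Both routes assume equal groups.

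**Step 2: why the split matters.** For a binary outcome the Kruskal-Wallis statistic is H = (N − 1)/N × Pearson chi-square on 2 df. With group A at distance d from B and C, the approximate noncentrality is

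λ = d² × [n_A × n_BC / N] / [p̄(1 − p̄)], where p̄ is the overall mortality.

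At 28/48/48%:
- 82/82/82: 82 × 164/246 = 54.67; p̄ = 0.4133; λ = 0.04 × 54.67/0.2425 = 9.02
- 53/106/106: 53 × 212/265 = 42.4; p̄ = 0.44; λ = 0.04 × 42.4/0.2464 = 6.88

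As B and C grow without limit, the bracket n_A × n_BC / N tends to n_A = 53 and p̄ to 0.48. Then λ tends to 0.04 × 53/0.2496 = 8.49, still below the 9.02 of equal groups of 82.

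**Step 3: power by full enumeration of the binomial outcomes at 28/48/48%.**

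| A/B/C | Power |
|---|---|
| 82/82/82 | 78% |
| 53/53/53 | 58% |
| 53/82/82 | 63% |
| **53/106/106** | **66%** |
| 53/200/200 | 71% |
| 53/300/300 | 73% |
| 78/106/106 | 80% |
| 50/106/106 | 64% |
| 48/106/106 (10% of A lost) | 62% |
| 48/95/95 (10% of every group lost) | 61% |

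The 10% loss is my assumption. Enlarging B and C helps (58% to 66%) but does not restore 80%, and it does not make good losses in A.

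**Step 4: vary the comparator mortality at 53/106/106.**

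| Comparators | Cocktail | Power |
|---|---|---|
| 30% | 10% | 83% |
| 32% | 12% | 80% |
| 35% | 15% | 76% |
| 40% | 20% | 71% |
| 48% | 28% | 66% |
| 60% | 40% | 65% |
| 80% | 60% | 76% |
| 85% | 65% | 82% |

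Power is below 80% from about 32% to about 83%.

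**Step 5: does the omnibus test address aim 1?** Set the cocktail at 48%, midway between B and C, so that it does not differ from their average. If B and C differ by 10, 15 or 20 points, the three-group test is significant in 24%, 49% or 75% of trials.

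**Step 6: a direct contrast with the same patients** (pooled z-test, two-sided 0.05, full enumeration):
- A versus B+C (53 versus 212): 77% at 48%, 81% at 40%. With 10% of A lost (48 versus 212): 73% at 48%.
- A versus B, or A versus C (53 versus 106): 68% each at 48%.
- Approximate 95% CI half-width for A versus B+C at 28% versus 48%: 1.96 × √(0.28 × 0.72/53 + 0.48 × 0.52/212) = 13.8 points.

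**Step 7: the other ratio.** At 2:1:1 (about 132/66/67) the omnibus power at 48% is 87%, but that needs about 132 cocktail patients against a supply of about 50.

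**The case against.** The strongest reply has four parts.

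*The 246 is not a miscalculation, and the supply limit is disclosed.* Both are true. On the 40%-versus-20% route, equal groups of 82 have 83% Kruskal-Wallis power. But the matching figure for 53/106/106 is 71%, so the claim still does not carry over to the design being run.

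*The 48% is soft.* It divides deaths from one period by an admission rate described as current. It is not a 28-day rate, and the trial excludes "patients expected to die within 48 hours". This stands as a limit on any single figure: at comparator mortality of about 32% or below, the planned test reaches 80%. The section offers no other mortality source, however, and the shortfall persists from about 32% to 83%. If the 20-point gap lay only between B and C, with A equal to one of them, power would be 85%, but that is not the aim 1 comparison.

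*For a direct contrast the deficit is small.* Cocktail versus pooled comparators has 77% at 48%, only 3 points short, and exceeds 80% at 40%. This is correct, but the plan does not name that contrast.

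*The proposed contrast has loose ends.* Logistic regression yields an odds ratio, not a risk difference. Pairwise comparisons raise multiplicity: at 0.025 each, power is 59% at 48%. Pooling is also a choice that aim 1 does not dictate. These points stand and are handled in the fix. The 2:1:1 ratio is probably a slip, given the supply, but it still needs correcting.

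**Conclusion.** The concern holds. The documents give no support for 80% power at 53/106/106. With the cocktail 20 points below both comparators, the planned test has about 66% power at 48% comparator mortality and 71% at 40%, before any loss to follow-up. The chance of missing such a benefit is then about 1 in 3 or 29%, against the 1 in 5 implied. These figures rest on the assumed pattern of differences and on a comparator rate the plan does not state. The direction changes only if that rate is at or below about 32%, or above about 83%.

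Independently of those assumptions, the only mortality test planned in all cases does not isolate the aim 1 comparison. Because mortality is the first primary outcome and the basis of the sample size, both points should be corrected before analysis.

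**What to change.** 1. **Restate the power.** Give it for 53/106/106 over a stated range of comparator mortality (83% at 30%, 71% at 40%, 66% at 48% for the three-group test, before losses), and say which groups are assumed to differ. Say that enlarging B and C partly offsets the supply-limited cocktail group, does not restore 80% at the derived 48%, and does not compensate for losses in group A.
2. **Name the primary mortality contrast.** Use group A versus B+C, as a risk difference with 95% CI. Show A versus B and A versus C beside it as descriptive estimates with intervals, or state a multiplicity rule if they are to be tested. Because the Method section calls the study non-RCT, report the logistic regression as the baseline-adjusted version of the same contrast in all cases. Either label its result as an odds ratio or convert it to a risk difference by averaging predicted risks.
3. **Reconcile the ratio** in Population (2:1:1) with Interventions, Table 2 and Sample Size (1:2:2).

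**Cost.** Sample-size and SAP wording only, with no more patients. The stated power becomes less favourable. The pooled contrast is still short of 80% at 48% mortality (77%, or 73% with 10% loss in A). It averages over two comparators, which is why the separate comparisons are shown. The powers quoted are for unadjusted comparisons.

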**Figure 2: Assignment of the included COVID cases at their groups.**

**Figure 3: Frequency of interventions in included patients**

## **Method:**

The type of this study is single blind non-RCT and is considered a Phase IV Clinical trial (post-marketing study) to report efficacy and safety of new medicine.

We use PubMed search tool to find clinical studies that performed to test efficacy and safety of developed immunotherapy in treatment of COVID-19 with about 4,000 results with focusing on antibodies developed as antiviral against COVID-19 obtaining only 70 results from which REGN-COV2, a Neutralizing Antibody Cocktail is selected with its only one clinical study up to now (REGN-COV2, a Neutralizing Antibody Cocktail, in Outpatients with Covid-19) which is published in New England Journal of Medicine on January 21, 2021.

Another resource used to obtain data is Fact Sheet for Health Care Providers-EUA OF casirivimab and imdevimab which provides clinical data about the use of this antibodies cocktail. Endnote citation software is used for citation of references.

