## **Outcomes:**

Parameters that will be assessed during hospitalization at day 0(baseline), day 3, 7, 14, 28 include:

- C-reactive protein (CRP)
- ferritin
- lactate dehydrogenase (LDH)
- D-dimer
- serum creatinine(S.Cr) and estimated creatinine clearance(CrCl)
- alanine aminotransferase (ALT), aspartate aminotransferase (AST), albumin, bilirubin

Clinical outcomes measured before & during intervention

1) Primary outcomes

- 1- 28-days mortality rate (efficacy).
- 2-PCR test results at end of hospital visit (efficacy).
- 3-precentage of patients who developed infusion related or hypersensitivity reactions during and after the end of drug infusion and reporting of any Serious and unexpected adverse events may occur that have not been previously reported with REGEN-COV use that may cause drug discontinuation (Safety).

2) Secondary outcomes

- 1-Need for invasive mechanical ventilation.
- 2- Invasive mechanical ventilation and oxygen support duration (days).
- 3- Time to clinical improvement (defined as 2 points reduction in the WHO disease ordinal progression scale(11&12) or discharge, whatever happens first)
- 4- ICU and hospitalization length of stay (days).
- 5- SOFA score(13) on day 0,3,7,14, and 28.
- 6- COVID19 WHO disease progression score(11&12) from day 0 to day 28.
- 7- Inflammatory markers including CRP, ferritin, LDH
- 8- liver and kidney functions

In addition to clinical outcomes measured before and during intervention, Vital signs, glasgow coma score (GCS),complete blood count (CBC), artierial blood gas (ABG) and prothrombin time (PT) is recorded at day0.

Patients' charactrestics(age,gender) and relevant medical and medication history and current COVID-19 treatment drugs will be recorded on admission

Duration of research will be about 6 months from Novmber 2021 to March 2022

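### If allocation is not concurrent randomisation, the limited cocktail stock could place group A in part of the study period, and the mortality analysis has no calendar term to guard against this

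*Combined protocol and SAP*

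**What the plan says.** **Supply and group sizes.** The Sample Size section enlarges the remdesivir and favipiravir groups "to be 106 patients compared to 53 patients in Antibodies cocktail Group", and gives the reason: "As Antibodies cocktail product is available for only about 50 COVID-19 patients". It adds that "the ratio (1:2:2) is the closest to reality according to number of patients who receive each drug". Table 2 shows the same 53, 106 and 106.

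**Allocation.** The Method section states: "The type of this study is single blind non-RCT". The Population section says that patients "will be randomized (2:1:1) into 3 groups", listing the cocktail first. The Interventions section says that they "will be assigned into 3 groups with 1:2:2 ratios". No section describes how a patient comes to be in a group, whether the three groups are enrolled side by side, or how the cocktail stock is spread over time.

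**Period.** The Outcomes section states: "Duration of research will be about 6 months from Novmber 2021 to March 2022". November to March is five calendar months.

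**Analysis.** The Statistical Analysis Plan compares 28-day mortality across the three groups with an unadjusted Kruskal-Wallis test. On adjustment it says: "In case of existing differences in some baseline characteristics, logistic regression will be performed". It names no covariate. The Outcomes section lists what is recorded at admission or day 0: age, gender, medical and medication history, current COVID-19 drugs, laboratory values, SOFA, WHO score, vital signs, Glasgow coma score and blood gases. Admission date or calendar period appears neither there nor in the analysis plan.

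**The concern.** With a small stock, one natural course is to treat consecutive eligible patients with the cocktail until it runs out, while the two comparators go on accruing. Group A then belongs to one part of the winter and groups B and C to all of it. If mortality changes over those months for reasons other than the study drugs, such as hospital load, the comparison between groups carries that change, in either direction.

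Concurrent randomisation at a fixed ratio would largely prevent this, but the documents contradict each other on whether patients are randomised. The analysis offers only partial protection. The primary test is unadjusted, and the regression depends on a baseline difference being found. A time trend that the day-0 variables do not capture, or that the baseline tests miss, stays in the mortality comparison.

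**Working it through.** **1. The plan's own figures.** The total of 246 is reproduced by a one-way ANOVA with three equal groups, Cohen's f = 0.2 and alpha 0.05: power at N = 246 is 0.804. This point does not rest on that figure. The background mortality used below is 120 deaths / 250 admissions per month = 48%. Both numbers are in the Sample Size section. Dividing them assumes that the current admission rate also held in August to October 2021.

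**2. Could group A fill in part of the period?** At 250 admissions per month, five to six months give 1,250 to 1,500 admissions for 265 places. The eligible and consenting share is not given, so it is varied. Let r = 250 × share. Time to fill A alone, if every such patient received the cocktail until it ran out, is 53/r months (× 30.4 days). Time for the whole sample is 265/r months.

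| Assumed share | 53 patients | 265 patients |
|---|---|---|
| 100% | 6 days | 1.1 months |
| 50% | 13 days | 2.1 months |
| 25% | 26 days | 4.2 months |
| 10% | 64 days | 10.6 months (exceeds the study) |

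So concentration is possible. At shares of 25% or more, A could fill within a month.

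**3. Bias from a time trend.** Assume two equal halves whose mortality differs by d around a mean of 48%, no drug effect, B and C spread evenly, and a fraction s of group A in the lower-mortality half. B and C then have expected mortality 48%, and A has 48% − (2s − 1) × d/2. For s = 1 the bias is d/2. For s = 0.75 it is d/4. If A falls in the higher-mortality half, the sign reverses.

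**4. False rejection by the planned test.** For a yes/no outcome the Kruskal-Wallis statistic is the Pearson chi-square on 2 degrees of freedom times (N − 1)/N = 264/265. Simulating 100,000 trials per setting with groups of 53, 106 and 106 gives 5.1% rejection with no trend, and otherwise:

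| d (points) | Bias, s = 1 | Rejection, s = 1 | Bias, s = 0.75 | Rejection, s = 0.75 |
|---|---|---|---|---|
| 5 | 2.5 | 5.9% | 1.25 | 5.2% |
| 10 | 5 | 8.3% | 2.5 | 5.8% |
| 15 | 7.5 | 12.8% | 3.75 | 6.9% |
| 20 | 10 | 19.5% | 5 | 8.3% |

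Check by formula for d = 10, s = 1: A is 0.43, and B and C are 0.48. Pooled mortality is (53 × 0.43 + 212 × 0.48)/265 = 0.47. Noncentrality is (53 × 0.04² + 212 × 0.01²)/(0.47 × 0.53) = 0.106/0.2491 = 0.43. The noncentral chi-square on 2 degrees of freedom then exceeds 5.99 with probability 8.3%, which agrees with the simulation.

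**5. Outer limit.** If A and the comparators were enrolled in entirely separate periods, the bias would be the full d, and rejection would be 8.3%, 19.5%, 40% and 66% for d = 5, 10, 15 and 20. Nothing in the documents suggests separation this complete.

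**The case against.** The strongest reply is that the Population section says that patients are randomised. If that statement governs and randomisation is concurrent, the problem largely disappears. This stands, and it is why the point is conditional. The statement cannot simply be relied on, though: it conflicts with the Method section on design, and with the Interventions section, Table 2 and the Sample Size section on ratio.

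The reply also has force elsewhere. B and C are fixed in number too, at 106 each. If nearly all admissions were eligible, the whole sample would be about 265/250 = 1.06 months of admissions, leaving little time for drift. The stated duration is that of the research, not of enrolment; with 28-day follow-up inside it, enrolment would be nearer four months. These facts reduce the likely size but do not supply a rule for concurrent enrolment.

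A reader might infer three stronger claims that the documents do not support:

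- That group A will be enrolled in one block. No section says so; it is only possible.
- That every change over the study months would count as a drug effect. Severity markers and current treatment are recorded at baseline, so a shift in them that shows up as a group difference can trigger adjustment. What remains is drift that those variables do not measure or the tests do not detect.
- That the plan restricts adjustment to a short list, or rules out admission date. The analysis plan names no covariate at all, so the date is omitted rather than excluded.

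**Conclusion.** The point holds in a conditional form and is minor. Randomised and non-RCT cannot both be right, and the sections must be reconciled. If allocation is anything other than concurrent randomisation, the plan has no safeguard in enrolment or in analysis against group A and its comparators coming from different parts of the study period.

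The size is not derivable, because the documents give no month-to-month mortality and no enrolment timetable. Under the assumptions in the working, inflation is noticeable only when concentration is strong and the trend is large: about 8% false rejection for a 10-point difference between halves and about 20% for a 20-point difference, with all of A in one half. With three quarters of A in one half, it stays between about 5% and 8%.

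**What to change.** 1. Reconcile the Population, Method and Interventions sections on whether patients are randomised and at what ratio, and state the allocation mechanism.
2. State that the 1:2:2 ratio of Table 2 is kept within each calendar period, for example each month.
3. Tabulate enrolment by month and group in the report.
4. In the Statistical Analysis Plan, always include admission month or date as a covariate in the mortality model, whatever the baseline tests show.

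The cost is a few sentences and slightly more analysis. Length of stay is already a secondary outcome, so admission dates have to be collected anyway. The real constraint is that B and C enrolment is tied to the time when cocktail is available. Concurrent enrolment of 265 patients in five months needs 265/1,250 = 21% of admissions to be eligible and consenting; in four months it needs 265/1,000 = 26.5%. The documents do not give this share, so it should be checked first.

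Concurrent enrolment is the essential part. If group A does not overlap in time with B and C, the covariate cannot separate drug from period.
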